4.8 Measurement of Patient Compliance

All dosing is supervised in the clinic or by home health administration. Dosing compliance will be determined from site records and entry into the eCRF. Patient compliance with study procedures at home will be estimated based on review of the patient's daily diary data at each visit. If the patient is less than 70% compliant with the requirements of the protocol based on review of their diary data, the Investigator or designee must determine if this is a training issue and retrain the patient on use of daily diary and pulmonary function device. If the patient continues to demonstrate poor compliance (< 70%), their participation should be reviewed with the contract research organization (CRO) and Sponsor to determine if the patient should be withdrawn from the study for failing to comply with the requirements of the protocol.

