5.5 Reasons for Patient Withdrawal

All patients have the right to withdraw from treatment or from the study at any time, for any reason, without prejudice. The Investigator may, but is not required to, discontinue any patient's study drug treatment for reasons of non-efficacy of the study drug or other reasons. The Investigator will notify the CRO and Sponsor of all decisions regarding withdrawal of the patient from treatment or from the study.

Patients will be encouraged to remain in the study and on treatment so long as there are no overarching safety concerns about their continued participation.

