5.7 Other Reasons as Withdrawal Criteria

The Investigator may also discontinue a patient's study drug treatment or study participation for reasons including, but not limited to, the following: AEs deemed by the Investigator to preclude continued study

Suzhou Connect Biopharmaceuticals, Ltd

Protocol CBP-201-WW003

Investigational Drug: CBP-201

21 December 2021

participation, protocol violations, withdrawal of consent, loss to follow-up, death of patient, or termination of the study by the Investigator or Sponsor.

Patients who develop any related grade 2 or higher cardiovascular, respiratory, or ophthalmic TEAE or any related grade 3 or higher TEAE involving other organ systems must be discontinued from further study drug treatment and monitored until resolution or stabilization.

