8 REPORTING ADVERSE EVENTS

8.1 Definitions

8.1.1 Adverse Event

An AE is defined as any untoward medical occurrence in a patient during a clinical study, whether or not it is related to the IP, at any time after the patient signs the ICF until Visit 17 (End of Study) or an Early Termination Visit, whichever occurs first.

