#### 4.11.2.2 Average Daily Nasal Congestion Score (NCS)

Daily Nasal Congestion Score (NCS) will be assessed by the patient through a patient diary from Visit 1 throughout the study by using a 0 to 3 categorical scale for severity of symptoms from none to severe over the past 24 hours.

Question: How would you rate nasal congestion over the last 24 hours?	
0	None
1	Minor
2	Moderate
3	Severe

Weekly mean of daily nasal congestion score will be calculated as sum of non-missing daily nasal congestion score divided by number of days with non-missing daily nasal congestion score using analysis window (Table ). The effect of treatment in terms of the change from Baseline week (i.e. average of 7 days prior to the baseline visit) to Week 24 (i.e. average of 7 days prior to the Week 24 visit) in average daily NCS will be also analyzed using Mixed-effect Model for Repeated Measures (MMRM).

The model will include treatment, presence of comorbid asthma, visit, treatment-by-visit interaction as categorical covariates, and average daily NCS at baseline as continuous covariates. Patient will be included as a random effect. An unstructured (UN) covariance matrix will be used to model the within-subject correlation. If this model fails to converge, then Akaike's Information Criterion (AIC) will be used to select the best covariance matrix among compound symmetry (CS), first-order autoregressive (AR(1)), and Toeplitz (TOEP). The treatment effect will be estimated using the difference between the treatments least squares means (adjusted means). The 95% confidence interval for the difference between the treatments least squares means and the p-value from the hypothesis test of no difference between the treatment groups will be also presented.

The sample SAS code for MMRM:

```
proc mixed data= data;
  class subjid cmabl trt01pn(ref='1') avisitn;
  model chg = trt01pn cmabl trt01pn*avisitn ncsbl*avisitn / ddfm=kr;
  repeated avisitn / subject=subjid type=UN;
  lsmeans trt01pn*avisit / pdiff cl alpha=0.05;
  ods output lsmeans=lsmeans diff=diffs;
run;
```

In addition to primary efficacy analysis summary, weekly mean of daily nasal congestion score will be summarized using descriptive statistics by treatment and overall.

A plot showing the LS mean of average daily NCS  $\pm$  SE bar over time within each treatment group will be provided.

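### Protocol 4.8 allows a randomised patient to be withdrawn from the whole study for poor diary compliance, which stops new AE recording and usually forfeits a Week 24 endoscopy that needs no diary

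*Protocol*

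**What the plan says.** Protocol 4.8 responds to poor diary compliance in two steps. Below 70%, the site decides whether training is the problem and retrains. After that, "If the patient continues to demonstrate poor compliance (< 70%), their participation should be reviewed with the contract research organization (CRO) and Sponsor", and the purpose of the review is "to determine if the patient should be withdrawn from the study for failing to comply with the requirements of the protocol". The rule is not confined to the run-in.

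Protocol 5.7 is broader: "The Investigator may also discontinue a patient's study drug treatment or study participation for reasons including, but not limited to, the following". Its list opens with AEs and goes on to "participation, protocol violations, withdrawal of consent, loss to follow-up, death of patient, or termination of the study".

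Other sections favour retention. Protocol 5.5 states: "Patients will be encouraged to remain in the study and on treatment so long as there are no overarching safety concerns about their continued participation". Sections 3.4 and 3.5 encourage patients who stop study drug to stay in the study, and 3.4 gives 8 weeks of follow-up after early discontinuation of drug. Section 5.6, on treatment failure, asks for all procedures unless consent is withdrawn or the patient is lost.

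A patient withdrawn from the study has an Early Termination visit whenever possible (5.8, 6.19) and is not replaced (5.9). AEs are collected "until Visit 17 (End of Study) or an Early Termination Visit, whichever occurs first" (8.1.1; 8.3 agrees).

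On the endpoints, Protocol 7.8.1 makes NPS a central reading of a clinic endoscopy video. SAP 4.11.2.2 defines weekly NCS as the sum of the available daily scores "divided by number of days with non-missing daily nasal congestion score", with no minimum number of days.

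**The concern.** The trigger is incomplete diary data, but the consequence reaches data that do not come from the diary. A patient who attends every visit but fills in the diary poorly can lose the Week 24 endoscopy, later laboratory, ECG and ADA assessments, and the post-treatment safety follow-up.

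Two things are at stake. First, diary completion may depend on how the patient feels: some may stop because they see no benefit, others because they feel well. Removal on that ground may therefore be informative, whereas the planned MMRM (SAP 4.11.1.2) assumes missing at random. Second, recording of new AEs ends at the Early Termination visit, although Protocol 9.6 counts treatment-emergent events to the end of follow-up and SAP 4.15 now centres the analysis on safety.

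**Working it through.** **1. What a removal costs, from the text.** Take a removal at Week 12 as an illustration.
- NPS still scheduled after that point: Weeks 16, 24 and 32. The Early Termination endoscopy replaces these with one reading.
- SAP 4.3.1, Table 3 assigns NPS to Week 24 only on days 163 to 169. An Early Termination endoscopy near day 85 falls outside, and no rule maps it to Week 24. Only a removal close to Week 24 would escape this.
- New AE recording stops about 20 weeks early (32 − 12 = 20).
- By comparison, under 3.4 a patient who stops study drug keeps 8 weeks of follow-up. This supports the point about AE follow-up. It does not by itself show that 3.4 secures a Week 24 NPS, since 3.4 brings the end-of-treatment assessments forward. A patient with a poor diary who is still being dosed is, however, already scheduled for the Week 24 visit.

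**2. Whether the analysis needs the removal.** NPS does not use the diary. For NCS, a patient with 4 of 7 entries has 4/7 = 57% compliance, fails the 70% rule, and still yields a weekly mean under SAP 4.11.2.2. Removal turns partial data into none.

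**3. The plan's sample size.** Inputs from Protocol 9.1 and SAP 4.14: difference 1.3, SD 2.1, two-sided alpha 0.05, power 80%, dropout 15%.
- n per group = 2 × (1.960 + 0.842)² × 2.1² / 1.3² = 40.96, rounded up to 41.
- Power at 41: standard error = 2.1 × √(2/41) = 0.4638; 1.3/0.4638 = 2.803; Φ(2.803 − 1.960) = 80.0% (79.1% with the noncentral t).
- Inflation: 41/0.85 = 48.2, rounded up to 49; 3 × 49 = 147.

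The plan's figures reproduce. The allowance is 49 − 41 = 8 patients per group.

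**4. Effect of removals.** The documents give no rate, so r below is an assumption. If removals are part of the 15%, evaluable n stays at 49 × 0.85 = 41.65 and nothing changes. If they are additional, evaluable n = 49 × (0.85 − r), and power = Φ(1.3 / (2.1 × √(2/n)) − 1.960):

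| Assumed extra removals r | Evaluable n per group | Power |
|---|---|---|
| 0 | 41.65 | 80.65% |
| 2% | 40.67 | 79.72% |
| 5% | 39.20 | 78.25% |
| 10% | 36.75 | 75.60% |

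The losses are 0.9, 2.4 and 5.0 points. This is an available-case calculation. MMRM would recover part of the loss from earlier visits, if missing at random holds.

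**The case against.** Much of the case on the other side stands.

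- **Removal is not automatic.** 4.8 asks for a case-by-case review after retraining, and 5.7 says may. Investigators and clinical staff are blinded (5.4). A reader might infer that arms would be depleted differently; nothing in the documents shows that.
- **Data are not thrown away.** A reader might infer that removal discards results. What has been collected is kept, the Early Termination visit includes endoscopy, laboratory tests, ECG, ADA and AE review, existing AEs are followed until resolved or stabilised (8.3), and SAEs judged related stay reportable afterwards (8.8). The loss is new AEs after that visit and, usually, the Week 24 value.
- **No absolute rule is broken.** 5.5 and 3.4 only encourage retention, 5.5 itself provides for withdrawal from the study, and the firmer wording in 5.6 covers treatment failure only. The Intention-to-Treat statement in SAP 4.6 concerns analysis as randomised, not follow-up.
- **The diary has uses.** It records daily mometasone, reliever use and worsening symptoms, and it is the only source of NCS, on which success also depends. That justifies review and retraining. It does not explain why endoscopy and AE follow-up should stop.
- **5.7 is not simply administrative.** Protocol 11.6 defines a violation to include non-adherence that puts the patient at significant additional risk. A reader might infer that participation should end only for withdrawn consent, loss to follow-up, death or study termination. The documents do not support that list: it would drop the AE ground in 5.7 and override a term that is partly about safety.
- **The size is uncertain.** Such removals may already lie within the 15%, and Protocol 9.1 allows the sample size to be adjusted if non-completion exceeds it.

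**Conclusion.** The point holds for 4.8 in a limited form. The protocol permits, without requiring, the end of all follow-up for a reason tied only to the diary. The usual result is a missing Week 24 NPS and truncated AE recording in a patient who could have supplied both. The wording is inconsistent with the retention text in 3.4, 5.5 and 5.6 and needs to be reconciled.

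The effect on planned power is nil if removals sit inside the 15% allowance. If they are additional, it is roughly 1 to 5 points at assumed rates of 2% to 10%. These rates are illustrations, and the calculation ignores what MMRM recovers. That the missing data would be informative is plausible but not shown.

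Under SAP 4.15 the trial was terminated early, no hypothesis is tested and no sensitivity analysis will be run. The 8-per-group allowance therefore no longer governs anything. What remains is the completeness of the safety data and the descriptive co-primary summaries, where in a small sample each avoidable loss is noticeable.

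**What to change.** Amend Protocol 4.8 so that diary compliance persistently below 70% after randomisation leads to retraining and a recorded deviation. Scheduled visits, the Week 24 endoscopy and AE follow-up would continue unless the patient withdraws consent, is lost to follow-up, or another ground in the protocol applies. The 70% entry criterion in 5.1 stays as it is.

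In 5.7, reconcile protocol violations, as a ground for ending study participation, with 3.4, 5.5, 5.6 and the definition in 11.6. Leave the AE ground and all study-drug decisions unchanged.

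The cost is a short amendment, which under Protocol 11.4 needs IRB/EC approval before it is applied. The downside is small: some weekly NCS means will rest on fewer days. If visits have already closed, use the discontinuation reasons in the disposition summary (SAP 4.5.1) to identify and report any patient removed on this ground, and correct the wording before it is reused.

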5 PATIENT ENROLLMENT

5.1 Inclusion Criteria

A patient must meet the following criteria to be eligible to participate in this study:

1. Female and male patients aged ≥ 18 and ≤ 75 years at the time of screening.
2. Patients who are diagnosed with chronic rhinosinusitis with bilateral polyps despite treatment with systemic corticosteroid within the past 2 years and/or medical contraindication/intolerance to systemic corticosteroids. The polyps have a minimum bilateral NPS of 5 out of a maximum score of 8 with at least a score of 2 for each nostril at screening (central read) and baseline (local read) evaluated by endoscopy. *Note: Patient intolerance to systemic corticosteroids includes patient refusal of treatment with systemic corticosteroids due to undesirable side effects.*
3. Nasal congestion/blockade/obstruction with moderate or severe symptom severity (Nasal Congestion Score of ≥ 2) at screening and a weekly average severity of > 1 at time of randomization.
4. Patients using nasal mometasone at least 200 mcg per day, or equivalent daily dosing of another INCS, for at least 28 days before randomization, and willing to continue for the duration of the study. *Note: For patients who are using an alternative INCS product other than MFNS prior to the screening visit, the investigator must switch the patient to MFNS at V1. Patients must use nasal mometasone at least 200 mcg/day, or equivalent, for at least 28 days before randomization, which can include 21 days prior to screening with supportive*

documentation. Run-in can be 7-31 days with the compliance determined in the week prior to dosing

5. Patients willing to enter patient diary daily symptom assessments and maintain stable dosing with MFNS with a compliance of at least 70% in the 7 days preceding randomization. *Note: 70% compliance will be calculated as at least 5 of 7 DAYS of MFNS use in the 7 days prior to randomization AND at least 5 of 7 DAYS of NCS completion in the patient diary in the 7 days prior to randomization.*
6. Male patients who are nonsterilized and sexually active with a female partner of childbearing potential agree to use highly effective contraception from randomization until 8 weeks after last dose.
7. Female patients of childbearing potential who are sexually active with a nonsterilized male partner should have a confirmed negative serum beta-human chorionic gonadotropin test at Visit 1 and agrees to use highly effective contraception from signing of informed consent throughout the duration of the study and for 8 weeks after last dose.
8. Patient able to read and understand and willing to sign the informed consent form (ICF) prior to any study related procedures being performed.
9. Willing and able to comply with study visits and study-related procedures, in the opinion of the Investigator.

5.2 Exclusion Criteria

A patient who meets any of the following criteria will be ineligible to participate in this study:

10. Patients unable to use MFNS.
11. Patients who are taking or have taken the following prohibited therapies as specified:
 - a. Systemic steroids within 28 days prior to screening
 - b. Other nonbiologic investigational drugs within 60 days (or 5 half-lives, whichever is longer) of screening,
 - c. Intranasal corticosteroid drops or CS-administering devices (eg, OptiNose device or stents) within 28 days prior to screening,
 - d. Non-steroidal immunosuppressants (eg, cyclosporine, methotrexate, azathioprine, mycophenolate, sirolimus, tacrolimus) within 60 days or 5 half-lives, whichever is longer, of screening,

- e. Any monoclonal antibody therapy (eg, benralizumab, mepolizumab, omalizumab, reslizumab, dupilumab) or investigational biologic drug for asthma or other diseases within 60 days or 5 half-lives, whichever is longer, of screening
- f. Leukotriene antagonists/modifiers within 7 days prior to screening for patients who were not on continuous treatment for \geq 30 days prior to screening
- g. Allergen immunotherapy for patients who were not on maintenance treatment for at least 90 days prior to screening
- h. Any marketed nonbiologic drug that modulates type 2 cytokines (eg, suplatast tosilate) within 30 days or 5 half-lives (whichever is longer) prior to screening
- i. Any investigational small molecule drug or treatment within 16 weeks or 5 half-lives (whichever is longer) prior to screening

12. Patients who did not respond favorably to previous dupilumab treatment (eg, therapy failure or patient experienced an adverse reaction to treatment).

13. Patients who have undergone any nasal surgery (including polypectomy) within 6 months before screening; or have a history of sinus or nasal surgery modifying the structure of the nose such that assessment of NPS is not possible or have had uncontrolled epistaxis requiring surgical or procedural intervention, including nasal packing.

14. Patients with conditions/concomitant diseases making them non evaluable at screening or for the primary efficacy endpoint such as: antrochoanal polyps, nasal septal deviation that would occlude at least 1 nostril, acute sinusitis, nasal infection or upper respiratory infection at screening or within 2 weeks before screening, ongoing rhinitis medicamentosa; known or suspected diagnosis of cystic fibrosis; chronic granulomatous disease and granulomatous vasculitis, granulomatosis with polyangiitis (Wegener's Granulomatosis), eosinophilic granulomatous with polyangiitis (Churg-Strauss syndrome), Young's syndrome, primary dyskinetic ciliary syndromes (eg, Kartagener's syndrome) or other dyskinetic ciliary syndromes.

15. Signs or a CT scan suggestive of Allergic Fungal Rhinosinusitis.

16. Patients with co-morbid asthma are excluded if:

- a. $FEV_1 \leq 50\%$ of normal predicted value.

OR

- b. An exacerbation within 90 days prior screening that required hospitalization (> 24 hours).

OR

- c. Are on a daily dose of inhaled corticosteroids (ICS) higher than 1000 mcg fluticasone propionate or the equivalent.

- 17. Known or suspected history of immunosuppression, including history of invasive opportunistic infections, such as aspergillosis, coccidioidomycosis, histoplasmosis, human immunodeficiency virus (HIV), listeriosis, pneumocystosis, or tuberculosis, despite infection resolution; or unusually frequent, recurrent or prolonged infections. Tuberculosis testing would be performed on a country by country basis according to local guidelines if required by regulatory authorities or ethics committees.
- 18. Patients who have active Hepatitis B, Hepatitis C or HIV infections as determined by positive results at Screening for hepatitis B surface antigen (HBsAg), or hepatitis B core antibody (HBcAb) or hepatitis C virus antibody (HCVAb); or positive HIV serology.
Note: Patients who test positive for HBcAb, negative for HBsAg and subsequently confirmed positive for HBsAb, indicating resolved natural infection (confirmed by negative HBV-DNA), may participate. Patients with positive HCVAb may participate if subsequent viral load is confirmed negative.
- 19. A helminth parasitic infection diagnosed within 24 weeks prior to the date of informed consent that has not been treated with, or has failed to respond to, standard of care therapy
- 20. Evidence of infection requiring treatment with systemic antibacterials, antivirals, antifungals, antiparasitics, or antiprotozoals within 7 days before baseline, or significant viral infections within 14 days before screening that may not have received antiviral treatment.
- 21. Live, attenuated vaccinations within 28 days prior to screening or planned live, attenuated vaccinations during the study.
- 22. Pregnant or intent to become pregnant during the study, or breast-feeding women.
- 23. Any disorder, including, but not limited to, cardiovascular, gastrointestinal, hepatic, renal, neurological, musculoskeletal, infectious, endocrine, metabolic, haematological, psychiatric, or major physical impairment that is not stable in the opinion of the investigator and may affect the safety of the patient throughout the study, or influence the findings of the studies or their interpretations, or impede the patient's ability to complete the entire duration of study.

24. Any clinically significant abnormal findings in physical examination, vital signs, safety lab tests during screening/run-in period, which in the opinion of the investigator, may put the patient at risk because of their participation in the study, or may influence the results of the study, or the patient's ability to complete entire duration of the study
25. Have any of the following laboratory abnormalities at Screening:
 - a. Eosinophils >1500 cells/mm³ (or 1.5×10^9 /L)
 - b. Platelets <100000 cells/mm³ (or 100×10^9 /L)
 - c. Creatine phosphokinase (CPK) > 10 upper limit of normal (ULN)
 - d. Alanine aminotransferase (ALT) > 2.5 times the ULN
 - e. Aspartate aminotransferase (AST) ≥ 2.5 times the ULN
 - f. Bilirubin ≥ 2 times the ULN
26. History of alcohol or drug abuse within 12 months prior to the date of informed consent
27. An allergy to L-histidine, trehalose or Tween (polysorbate) 80 or a history of a systemic hypersensitivity reaction, other than localized injection site reaction, to any biologic drug
28. Plans to undergo any surgical procedures requiring general anesthesia during the study.
29. History of cancer: Patients who have had basal cell carcinoma, localized squamous cell carcinoma of the skin, or in situ carcinoma of the cervix are eligible provided that the patient is in remission and curative therapy was completed at least 12 months prior to the date informed consent. *Note: Patients who have had other malignancies are eligible provided that the patient is in remission and curative therapy was completed at least 5 years prior to the date informed consent.*

5.3 Randomisation Procedures

At Screening (Visit 1), potential study patients will be assigned a patient number by site personnel. The patient number is a 6-digit number consisting of a single digit country code, a 2-digit site identifier, and a sequential 3-digit patient number (eg, 3-02-001 for the first screened patient in country 3 at site 02, 3-05-002 for the second screened patient in country 3 at site 05).

All patients eligible for the double-blind phase of the study will be randomly assigned to receive 1 of 3 treatments: CBP-201 300 mg SC every 2 weeks, CBP-201 300 mg SC every 4 weeks or volume-matched placebo every 2 weeks.

Approximately 50% of the randomised patients will be targeted to have comorbid asthma, defined as $\geq 12\%$ reversibility and use of ICS $\leq 1000\text{ug/day}$. *Note: This may be demonstrated with a documented medical history of $\geq 12\%$ reversibility (improvement in FEV₁) within the previous 12 months or may be demonstrated at screening in the clinic. Patients may repeat the reversibility on a different day if it is determined that a longer bronchodilator washout period is needed.*

At least 50% of the randomized patients will be targeted to have type 2 inflammation marked by baseline blood eosinophil count $\geq 300 \text{ cells}/\mu\text{L}$. *As this is only a target, there will be no hard stop to recruitment but when the study begins to approach 35% patients with eosinophils $< 299 \text{ cells}/\mu\text{L}$, sites will be encouraged to identify more patients with $\geq 300 \text{ cells}/\mu\text{L}$.*

As patients qualify for randomization, they will be assigned to treatment by Interactive Voice/Web Response System. The random treatment assignments will be done in a 1:1:1 ratio. Allocation of each treatment will be balanced by the presence of comorbid asthma.

- Recruitment of NP patients without co-morbid asthma will stop when approximately 66 patients without asthma are randomized, and
- Patients with co-morbid asthma will continue to be randomized to complete a total number of 147 randomized NP patients.

Note: A screen-failed patient may be re-screened at the Investigator's discretion, at least 28 days after the original screening date. If re-screened, the patient should be considered under a new patient number.

